key criteria for Inclusion and Exclusion:	
1. Subjects aged 13-17
 
2. Major Depressive Disorder (MDD) or Treatment Resistant Depression (TRD) by a score of >17 on Hamilton Depression Rating Scale (HAM-D) and >40 on Children's Depression Rating Scale Revised (CDRS-R)
 
Exclusion Criteria
 
1. Subjects with metallic implants, brain injury, seizure disorder
 
2. Current or lifetime history of an eating disorder, psychosis, bipolar disorder, substance abuse

	
3. Current inpatient psychiatric hospitalization, or current symptoms (including suicide ideation) that would require inpatient hospitalization
 
4. Pregnancy for female subjects
 
5. Any other condition investigators deem may interfere with study participation or safety

Number Of Subjects	5
Study Duration	
Participation will last 17 weeks. Treatment will occur 5 days a week for 4 weeks. 3 Follow-up visits will be performed.
 
Study will recruit for 1 year.

Study Phases	(1) Screening : screening for eligibility and obtaining consent
Screening	(2) Intervention : subjects will receive iTBS, 5 days a week for 4 weeks
Study Treatment	(3) Follow up : a follow up visit will be done at 1 week, 4 weeks, and 12 weeks after the last treatment session.
Follow-Up	
Efficacy Evaluations	Evaluations of CDRS-R (Children's Depressive Rating Scale Revised) and HAM-D (Hamilton Depression rating scale) scores will be used to measure efficacy. MMSE, Trails B, list generation, Columbia Suicide Scale, semi-structured interviews for Non-suicidal Self Injurious Behavior (NSSIB), and medical review will be used to evaluate safety. Assessment of the number and per cent treatments completed and number and percent of subjects who withdraw from treatment will be used to assess feasibility
Pharmacokinetic Evaluations	N/A

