In this study we will investigate the **efficacy and durability** of the effects of iTBS in adolescent depression (see Specific AIM 1 below) by measuring changes in clinical ratings [CDRS-R, HAM-D, and Non-suicidal Self Injurious Behavior (NSSIB) evaluations] before and after 4 weeks of treatment, as well as 12 weeks following treatment. We expect that subjects will show: improvement in symptoms over 20 iTBS sessions as measured by the Children's Depression Rating Scale Revised (CDRS-R), HAM-D and Non-suicidal Self Injurious Behavior (NSSIB) measures, and persistence of this reduction of depressive symptoms through the 12 weeks follow up period of the study. In this study, we will investigate the **safety** of the effects of iTBS in adolescent depression (see Specific Aim 2 below). We will investigate safety of the treatment regimen by assessing suicidality. We expect suicidal thoughts and behavior will reduce with iTBS treatment as measured by the Columbia Suicide Severity Rating Scale (C-SSRS) and a psychiatrist's clinical assessment. We also expect that those with NSSIB at the start of the trial will have less after iTBS treatments. We do not expect any change in cognition measured with MMSE, Trails B, and list generation. We will investigate treatment feasibility by assessing treatment completion and withdrawal (See Specific Aim 3 below). We define the feasibility of iTBS will be defined as feasible by as completion of 15/20 (75%) iTBS treatment sessions by all subjects **AND** withdrawal from treatment of no more than one of five subjects (20%) due to intolerable side effects or persistent symptoms of

MDD. Investigation of efficacy, durability, safety as well as feasibility simultaneously is essential in this preliminary study of the use of iTBS in adolescents in order to justify a larger future study.

Non-Clinical and Clinical Study Findings

Potential Risks:

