2.0 STUDY OBJECTIVE

The purpose of the study is to determine the efficacy/durability, the safety, and the feasibility of iTBS in 5 adolescents with MDD.

Specific Aims.

Aim 1. Investigate the efficacy and durability of effects by estimating the magnitudes of pre-regimen vs. post-regimen longitudinal changes in CDRS-R, HAM-D, and NSSIB evaluations.

Hypothesis 1: Adolescents with MDD will show improvement in symptoms over 20 iTBS sessions as measured by the Children's Depression Rating Scale Revised (CDRS-R), HAM-D and NSSIB measures.

Hypothesis 2: Adolescents with MDD will show reduction of depressive symptoms will persists through the 12 week follow up period of the study.

Hypothesis 3: Adolescents with MDD who demonstrate NSSIB at the start of the trial will show reduction in NSSIB after iTBS treatments.

Aim 2. Investigate safety of the treatment regimen by assessing suicidality with the Columbia Suicide Severity Rating Scale (C-SSRS).

Hypothesis 1: Adolescents with MDD will show reduction in suicidal thoughts and behavior with iTBS treatment as measured by the Columbia Suicide Severity Rating Scale (C-SSRS) and a psychiatrist's clinical assessment.

Aim 3. Investigate treatment feasibility by assessing treatment completion and withdrawal.

Hypothesis 1: iTBS will be considered feasible if: a.) 15/20 (75%) iTBS treatment sessions are completed by all subjects, and; b.) no more than one of five subjects (20%) withdraw from iTBS due to intolerable side effects or persistent symptoms of MDD.

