4.2 Intervention/Treatment procedures (by visits)

- On the first treatment day: Prior to initiation of iTBS administration, the physician will establish 100% of motor threshold. iTBS will then be administered starting at 100% of motor threshold, increasing to 120% of motor threshold while adjusting the coil position to minimize side effects.
- The remaining 19 iTBS treatments: These will be delivered over a four week period, with five treatments delivered weekly by a UNC rTMS-trained physician Monday through Friday.
- General information about the entire treatment phase of study that is not visit specific: Each treatment will follow the iTBS protocols established by MagVenture, Inc. and treatment will be provided at 120% of motor threshold at all 20 treatment visits.
- Patients will undergo CDRS-R, HAM-D, and cognitive assessments once weekly during the treatment phase, starting on their fifth treatment day, and each week from that time point depending on which day of the week they start treatment.
- Patients will be assessed prior to every treatment for side effects or safety-related symptoms, as well as review of concomitant medication.

- Vitals will be taken prior to every treatment administration during all 20 treatment days. Weight will be obtained once per week during the treatment phase. Per investigator discretion, weight may be obtained at additional timepoints during the treatment phase or unscheduled visits to ensure safety of the subject.
- UDS and urine pregnancy tests can be done at any time due to investigator discretion for safety purposes. Pregnancy risk assessment will be documented at every visit for females of childbearing potential.

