4.6 Rescue medication administration: N/A

4.7 Subject Completion / Withdrawal procedures

Subjects who complete the study will be reminded of the study team's contact information should they have any questions in the future. Files will be kept under lock and key in a locked office in a secure facility for the

required amount of time according to GCP (Good Clinical Practice) principles and FDA regulations. For those wishing to withdraw from the study early, a termination visit will be scheduled to ensure safety, proper follow up, review adverse effects, and medications. CDRS-R, HAM-D, all cognitive, and safety assessments will be performed for final data capture if the patient agrees.

Patients will be withdrawn by investigators if they miss 20% of planned treatments, for noncompliance, or any other issues the PI determines can cause harm to the patient.

We will not replace discontinued participants. We will use the data we have up until discontinuation.

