8.0 STUDY INTERVENTION ADMINISTRATION

Treatment compliance and Adherence: A medication review will be performed prior to each treatment administration for treatment compliance. If 20% of planned sessions are missed, contraindicated medications are used, or there is worsening or lack of benefit, investigators can remove subject from the study. A trained study clinician will do administration of treatment.

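### Section 4.7 withdraws a subject at 4 missed sessions while feasibility criterion (a) tolerates 5, and section 8.0 makes the same removal optional, so the rule applied can decide the feasibility verdict

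*Combined protocol and SAP*

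**What the plan says.** Section 2.0 (Aim 3, Hypothesis 1) sets two conditions, both required: "15/20 (75%) iTBS treatment sessions are completed by all subjects, and; b.) no more than one of five subjects (20%) withdraw from iTBS", where the withdrawals counted are those due to intolerable side effects or persistent symptoms of depression. Section 1.2 repeats the first condition as "completion of 15/20 (75%) iTBS treatment sessions by all subjects" and joins the two with AND.

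Section 4.7 states: "Patients will be withdrawn by investigators if they miss 20% of planned treatments". It also provides for withdrawal for noncompliance and for "any other issues the PI determines can cause harm to the patient", and adds: "We will not replace discontinued participants".

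Section 8.0 uses the same threshold with a permissive verb: "If 20% of planned sessions are missed, contraindicated medications are used, or there is worsening or lack of benefit, investigators can remove subject".

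Section 4.2 describes the treatments after the first as "delivered over a four week period, with five treatments delivered weekly", and section 7.0 gives the total as 20 sessions. No make-up sessions are described. The synopsis says that the number and percent of treatments completed and the "number and percent of subjects who withdraw from treatment will be used to assess feasibility".

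**The concern.** The withdrawal rule and the success criterion use the same quantity, missed sessions, with different limits, and the withdrawal limit is reached first. A subject on course to satisfy (a) can be stopped by the protocol and then counted as failing it. Because 4.7 obliges and 8.0 only permits, two investigators with the same attendance record could each follow the protocol and reach opposite results.

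Aim 3 holds the plan's only numeric feasibility criterion. With five subjects, no replacement and a requirement on all subjects, one such removal changes the study's result to not feasible. That result would partly reflect the removal rule rather than whether adolescents can attend the course.

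**Working it through.** **Inputs.** 20 planned sessions (sections 4.2 and 7.0); 5 subjects (3.3); at least 15 sessions by all subjects (2.0, 1.2); trigger at 20% missed (4.7, 8.0).

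**The plan's own figures.** 15/20 = 75% and 1/5 = 20%; both reproduce.

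**The two limits.** Criterion (a) tolerates 20 − 15 = 5 missed. The trigger is 0.20 × 20 = 4 missed, one session tighter.

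**Where a strictly removed subject ends.** If the fourth miss falls at session s, completed sessions = s − 4.
- s = 4 to 18: 0 to 14 completed, so (a) fails.
- s = 19: 15 completed, so (a) is met.
- s = 20: 16 completed, so (a) is met.

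Otherwise a subject must miss no more than 3, that is complete 17/20 = 85%.

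**Counting attendance records that pass (a) if treatment continues.**
- Exactly 4 misses: C(20,4) = 4,845 placements. Strict removal fails those with all four misses in the first 18 sessions: C(18,4) = 3,060 (63%).
- Exactly 5 misses: C(20,5) = 15,504 placements. Only those with the fourth and fifth misses at sessions 19 and 20 survive, C(18,3) = 816, so 15,504 − 816 = 14,688 fail (95%).

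**Which trigger removes the problem.**
- Fifth miss (25%): 0 of 4,845 fail, but a fifth miss at session s leaves s − 5 completed, below 15 for s up to 19. So C(19,5) = 11,628 of 15,504 (75%) still fail.
- Sixth miss: 0 and 0 fail. At that point at most 20 − 6 = 14 sessions are attainable, so (a) is already lost.

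**Illustration of size.** The documents give no attendance rate. Assume independent sessions, each attended with probability p.
- No removal, or removal at the sixth miss: q = Σ (j = 0 to 5) C(20,j)(1−p)^j p^(20−j).
- Strict 4.7: q = P(at most 3 misses) + C(18,3)(1−p)⁴p¹⁵ + C(19,3)(1−p)⁴p¹⁶.
- At p = 0.90, strict: 0.8670 + 0.0168 + 0.0180 = 0.9018; all five subjects: 0.9018⁵ = 0.596.

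| Assumed p | One subject, strict 4.7 | One subject, no removal | All five, strict 4.7 | All five, no removal |
|---|---|---|---|---|
| 0.85 | 0.720 | 0.933 | 0.194 | 0.706 |
| 0.90 | 0.902 | 0.989 | 0.596 | 0.945 |
| 0.95 | 0.989 | 0.9997 | 0.947 | 0.998 |

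The placement counts are exact but are not probabilities. The table is only as good as its assumed attendance and independence.

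**The case against.** The strongest reply is that the two rules do different jobs. Section 4.7 is a compliance rule for a subject and Aim 3 is a verdict on the study, so a discontinuation rule stricter than the success bar need not be a contradiction. A subject removed for missed visits has attended poorly, and recording that is what Aim 3 is for. This has some force, but it does not explain why the criterion names 75% when strict removal delivers 85% for most patterns, and no section gives a reason, such as minimum exposure, for the tighter limit. Nor does it reconcile the obligation in 4.7 with the option in 8.0.

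A second reply is that using the permissive verb in both sections would be enough. That would remove the conflict, but it would leave a discretionary decision in an open-label study able to settle the verdict. Raising (a) to 17 of 20 would also align the rules, at the price of changing the sponsor's stated 75%.

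A third reply is that the probabilities depend on assumed attendance and on there being no make-up sessions. This stands: the loss runs from 0.998 − 0.947 = 0.051 at 95% attendance to 0.706 − 0.194 = 0.512 at 85%, and it is nil if investigators use 8.0 not to remove.

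A reader might also infer that (a) and (b) contradict each other, or that (b) is empty. The documents do not support that. The two are joined by AND, so (b) is a further cap, and overlap between joint conditions is not an error. Read literally, a subject who stops before 15 completed sessions already fails (a), so (b) adds a limit only for stops after 15 to 19 sessions. It still binds there: two side-effect stops in that range pass (a) and fail (b). The documents do not say whether an early withdrawal was meant to be tolerated.

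**Conclusion.** The point holds as a misalignment of wording. Section 4.7 followed strictly makes the effective bar at most 3 missed sessions, except when the fourth miss falls at session 19 or 20, while section 8.0 lets the same record pass. The arithmetic rests on reading 20% as 4 of 20, on all subjects including those withdrawn, and on no make-up sessions. A removal for missed sessions is not among the reasons counted in (b), so it acts only through (a).

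Severity is minor to moderate. It would go too far to say that feasibility is undefined, since a verdict follows once one section is chosen, or that the study is likely to fail it, since no attendance rate is given. Section 1.2 links feasibility to justifying a larger study, but no section sets a go/no-go rule. Raw completion and withdrawal counts will be available in any case, and the depression endpoints and safety stopping do not depend on the verdict.

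**What to change.** Use one trigger in sections 4.7 and 8.0, for example: *Subjects who miss more than 5 of the 20 planned sessions will be withdrawn.* Removal for missed sessions then cannot change the verdict on (a). Moving the trigger only to 25% would not achieve this.

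Split the sentence in 8.0 so that the mandatory verb applies to this trigger alone, and keep removal for contraindicated medication, worsening or lack of benefit discretionary. Keep the harm and noncompliance clauses of 4.7, and state that missing 5 or fewer sessions is not by itself noncompliance.

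The cost is wording, plus some subjects treated at reduced exposure. Those kept on beyond the present trigger are the subjects whose fourth miss falls by session 19. With independent attendance p, that share is P(Binomial(19, 1−p) ≥ 4): 31.6%, 11.5% or 1.3% at an assumed 85%, 90% or 95%. This slightly dilutes the 20-session course on which Aim 1 is framed.

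Relaxing (a) to 4 of 5 subjects would let the criteria absorb one early withdrawal, but it is a more lenient standard and the sponsor's choice, not a correction. Any change should be made before data are seen.

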3.0 INVESTIGATIONAL PLAN (brief overview)

3.1 Study Design

Type of design: A pilot study that is an open label, feasibility study. This study will aim to reduce depressive symptoms in adolescents using iTBS and evaluating the safety of methods. This will be an uncontrolled study design.

The study phases are described below:

- **Screening/Baseline:** This will include informed consent, an Intake Assessment (including psychological assessments / questionnaires), medical review with physical exam, vitals, UDS, and pregnancy screening for a total of about 2 hours, and needed collateral. Screening will last up to 1 week prior to scheduling first treatment session in order to allow sufficient time to gather all needed medical information. The entire screening visit itself should last up to 3 hours with patient and caregiver.
- **Intervention/Treatment:** Participants will receive iTBS immediately following screening, should they be determined eligible. Treatment visits will last 20 days, Monday-Friday for approximately 10 minutes each session. Although the actual procedure takes 3 minutes, we estimate close to 5-7 minutes will be required for setting up the treatment and the equipment. Treatment will occur over a 4-week period. Once per week, additional cognitive and safety assessments will be performed. During the last the day of the treatment phase, efficacy and safety scales will be performed also. Subjects will continue to receive routine psychiatric care from their outpatient mental health team, which may consist of a psychiatrist and a therapist.

- **Follow up:** There will be 3 follow up appointments to evaluate long-term efficacy and safety at 1 week, 4 weeks, and 12 weeks since the last treatment session.
- **Unscheduled Visits:** These will be done for any safety concerns and may include any of the assessments listed above. If pregnancy is suspected, another urine pregnancy test will be performed.

3.2 Allocation to Treatment Groups and Blinding (if applicable): N/A

3.3 Study Duration, Enrollment and Number of Subjects

5 subjects are expected to enroll. The total study participation will be over the course of 16-17 weeks, including the 24 study visits. The iTBS treatment itself will last a few minutes, and additional time will be allocated for machine set-up and additional review of symptoms as needed. Once per week during the treatment phase, subjects will also have additional cognitive and safety assessments done for safety monitoring that will last approximately 1 hour.

Given that subjects will need to come in 4 consecutive weeks Monday-Friday for treatments, it is likely one patient will be treated at a time. With the need to enroll and complete all data collection within a year, minus startup time, it is feasible to enroll 5 patients. In addition, iTBS has not been used in patients younger than 16 before, and while there is no safety concern for this, it would make sense from a safety perspective to start with a smaller number of participants. The data used from this study will then be used to pursue larger grant opportunities such as R01 to enroll more subjects that will allow for statistical significance calculations.

3.4 Study Population

Inclusion Criteria:

- A score of greater than 40 on the CDRS-R and 17 on HAM-D.
- Documentation of DSM-V criteria for current MDD or TRD will be required for study entry.
- Patients may be on antidepressant medication at a stable dose or receiving psychotherapy with a licensed provider during the active phase of TMS treatment for 4 weeks.
- Ability to provide consent and take part in questionnaires and scales (i.e.: not currently intellectually disabled).
- The presence of suicidality or NSSIB are not required to enter this study. Although our secondary endpoints include suicidality, and we are also exploring NSSIB, and thus this may not lead to many data, the investigators' plan is to use data from this study to justify a larger study where this can be more robustly investigated.

Exclusionary criteria:

- Past or current diagnosis of bipolar disorder, psychosis, seizures or traumatic brain injury.
- Presence of intracranial metallic implants or fragments, which is a contraindication for TMS.

- Lifetime history of (or currently present) epilepsy.
- Current diagnosis of substance abuse, eating disorder, PTSD (Post Traumatic Stress Disorder), or intellectual disability.* Nicotine use disorder will not directly preclude a potential subject from this study. Although chronic nicotine use does effect central nervous system excitability, [23] what would be more confounding to our study would be if there is a sudden change in nicotine use during the treatment phase, as this may affect the motor threshold. Inclusion will however be at the PI's discretion.
- Current imminent suicide ideation or other clinical reasons for inpatient psychiatric hospitalization.
- Currently pregnant. There is currently not adequate data from this population to ensure safety with the scope of this protocol.
- Any reason the investigator determines may cause noncompliance with study rules or is unfit for receiving treatment.
- Currently taking certain medications including antidepressants, stimulants, benzodiazepines, and antipsychotics, antiepileptic (see Appendix A).
- Any positive drug testing from a urine drug test unless medically indicated with a valid prescription.

*Those with marijuana/cannabis positive results may retest later if at that time they do not meet criteria for substance abuse at screening and agree to refrain from use for the duration of study participation. Decision to be made by Investigator discretion.

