1.0 BACKGROUND AND RATIONALE

1.1 Introduction

Major depression disorder (MDD) in adolescents is a very common neuropsychiatric disorder. [1] Left untreated, adolescent MDD can severely affect relationships, the ability to participate in extracurricular activities, academics, as well as social functioning.[1,2] In adolescents with MDD left untreated, the condition can affect the cognitive and emotional trajectory towards adulthood. In the worst-case scenario, adolescent MDD can lead to suicide. [1,2]

Current psychiatric treatment options for adolescent MDD include psychotherapy, medications and ECT. [3] While effective, there are limitations for those requiring more rapid stabilization or with limited access to trained therapists in their community. Psychotropic medications for adolescent MDD are typically offered as first line treatment for teens with severe symptoms. [3] Side effects and concern about increased suicidality limit the acceptance of medication by teens and their parents. ECT is effective; however, it is associated with significant adverse effects (anesthesia complications, memory deficits, and headache, nausea and vomiting, memory deficits). The effect of ECT on the developing adolescent brain is unknown, rendering ECT a less desirable treatment choice in this population. [4a] Close to 30-40% of adolescents do not respond to the first round of accepted treatment strategies including antidepressants and psychotherapy. [4b] Of these patients, only half will then respond to a second treatment strategy, including a change in antidepressant. [5] Those that do not respond to two standard treatment regimens may be considered as having "Treatment Resistant Depression (TRD)" [5].

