- Serious side effects (seizures): 0% in kids treated with iTBS in studies performed so far. The risk for seizure increases if someone has central nervous system disorders or a history of epilepsy. In regular Transcranial Magnetic Stimulation (TMS), the risk is .06%

There is no known risk for increasing suicidality by using iTBS. In addition, patients who are imminently suicidal will not be allowed to participate in the study. Appropriate referrals will be made should this happen.

Potential Benefits:

Potential benefits include a reduction in depressive symptoms. This in turn can alleviate other impairments in functioning that are caused by depression; such as better sleep, appetite, socialization, school and work functioning, and overall wellness. This will be measured and tracked through HAM-D and CDRS-R assessments (more information on these assessments in section 5.2)

Additional Follow-up: Patients will continue to be seen by their regular provider and specialist, and may find benefit in working with an additional treatment team for closer follow-up.

Risk /Benefit Assessment

Due to the need to expand treatment for MDD and similarities between the risks and benefits to other treatment options currently available or other clinical studies, it has been determined that the potential benefits outweigh the potential risks.

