6.2 Secondary Endpoint

- To evaluate the reduction of suicidality in adolescents with MDD: This will be done with descriptive and repeated measures ANOVA.
- To assess durability of antidepressant effect: This will be done with descriptive and repeated measures ANOVA.
- To evaluate the change in Non-suicidal Self Injurious Behavior (NSSIB): This will be evaluated with descriptive statistics.
- Evaluation of adverse events will be performed at every visit and documented according to GCP guidelines. Appropriate follow up and referrals will be made as needed.

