6.3 Statistical Methods

- **Baseline Data:** CDRS-R, HAM-D, and other cognitive and safety assessments will be used at screening to capture baseline data.
- **Efficacy Analysis:** As this is an uncontrolled study design, the investigators understand that any change in scores or observed improvement in symptoms may not be necessarily attributable to the treatment received. Thus, efficacy analysis will be described in this context. The investigators feel that a larger study would be indicated which may be sham controlled. Repeated measures ANOVA will be used to compare depression rating scores from each of the treatment weeks compared to baseline, as well as comparing scores between follow up visits and baseline and end of treatment weeks. Pearson's r coefficient will be used to determine correlation between, CSSR-S scores, and primary endpoints (CDRS-R & HAM-D). Descriptive statistics to identify if NSSIB is present since the subject's last visit at baseline, during the interventional period and follow ups, will be used. It is worth noting that use of ANOVA analysis has been recommended by a biostatistician, but due to a small sample size, longitudinal data will not have adequate statistical power. In addition, confidence intervals will be large and results will be uninformative regarding statistical power. This uncertainty may contribute to a future study sample size that is still too small for statistical power, but a larger sample size than this protocol.
- **Pharmacokinetic Analysis:** N/A
- **Safety Analysis:** Measurement of safety is a continuous process starting with screening. Medical review of symptoms occurs at every visit. In addition, should safety concerns related to study treatment occur, additional unscheduled safety visits can be performed. Additional assessments are done weekly during the 4-week treatment phase.
- **Personnel:** Study coordinator will complete data entry into RedCap system and oversee data management. The Principle Investigator will do oversight. A TraCS biostatistician ([name]) will complete data analysis and computations and will work with the study team throughout the duration of study activities and completion.

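### No analysis rule covers antidepressant treatment or psychotherapy changed after the last iTBS session, so a re-treated relapse can count as 12-week durability

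*Combined protocol and SAP*

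**What the plan says.** **The question.** Aim 1 Hypothesis 2 (section 2.0) expects that "reduction of depressive symptoms will persists through the 12 week follow up period of the study". Section 6.2 makes it a secondary endpoint: "To assess durability of antidepressant effect: This will be done with descriptive and repeated measures ANOVA". Section 6.3 describes the contrasts as "comparing scores between follow up visits and baseline and end of treatment weeks". Section 3.1 and Appendix B place the follow-up ratings 1, 4 and 12 weeks after the last session (V22, V23, V24).

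**Other treatment.** The inclusion criterion in 3.4 allows antidepressants "at a stable dose or receiving psychotherapy with a licensed provider during the active phase of TMS treatment for 4 weeks". It sets no matching condition for follow-up. The Potential Benefits text in section 1 says, with no end date, "Patients will continue to be seen by their regular provider and specialist". Section 3.1 adds "Subjects will continue to receive routine psychiatric care from their outpatient mental health team", although that sentence stands in the treatment-phase bullet.

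**Other passages on medication.** Section 4.5 lists antidepressants among the drugs that rule out starting or continuing the study. Section 8.0 lets investigators remove a subject for contraindicated medication, worsening or lack of benefit. Section 4.7 uses data only up to discontinuation and does not replace subjects. Appendix A leaves antidepressants to investigator discretion, apart from tricyclics before screening.

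**Recording.** Medication is recorded at every visit (4.5, Appendix B), and 4.3 lists a review of concomitant therapy at all three follow-up visits. Nothing in 6.1 to 6.3 uses these records.

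**The concern.** Durability asks whether the benefit present at the last treatment visit (V21) holds. Subjects whose benefit fades are the ones most likely to be offered something new by their own psychiatrist or therapist. If that treatment works, the V24 score falls again, and the planned contrasts cannot tell this subject from one who stayed well on iTBS alone. The error is therefore directional.

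Durability is in the study title, and sections 3.3 and 6.4 say the data are meant to support a larger grant application. With five subjects, one such case is a fifth of the evidence.

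**Working it through.** The plan states no figure for durability, re-treatment or effect size, so there is nothing to reproduce. The check sets out what the plan does with a re-treated relapse, then sizes it under stated assumptions.

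**1. How much of the study is exposed.** Four treatment weeks plus 12 follow-up weeks make 16. The share in follow-up is 12/16 = 75%. Post-baseline ratings are 4 weekly plus 3 at follow-up, so 3/7 = 43% fall after the last session.

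**2. Two readings of the text for a subject who relapses and starts an antidepressant after V21.**
- *Reading A: 3.4 and Appendix A govern.* The subject stays, and all later scores enter the ANOVA. Improvement by V24 counts toward persistence.
- *Reading B: 4.5 and 8.0 are applied in follow-up.* The subject leaves, later scores are missing, and V24 rests on those remaining. Section 6.3 handles missing data only by a remark in the results and discussion.

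New psychotherapy falls under Reading A either way, since 4.5 and Appendix A concern drugs only.

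**3. Effect on the mean (Reading A).** If one relapse of d points is masked, the five-subject mean change is overstated by d/5. Values of d are assumed.

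| d (CDRS-R points) | one masked relapse | two masked relapses |
|---|---|---|
| 10 | 10/5 = 2 | 4 |
| 20 | 20/5 = 4 | 8 |
| 30 | 30/5 = 6 | 12 |

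Example: all five subjects are scored at -20. If one of them had relapsed to no change before re-treatment, the mean with that relapse counted is (4 × -20 + 0)/5 = -16.

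**4. Effect on a persistence count.** Section 1.1 gives "Close to 30-40% of adolescents do not respond to the first round of accepted treatment strategies including antidepressants and psychotherapy", which implies 60-70% response, and says half of the non-responders respond to a second strategy. Assume 2 of 5 subjects relapse and both are re-treated. Without re-treatment, persistence is 3/5 = 60%. Expected apparent persistence is (3 + 2r)/5, where r is the chance of response by V24:
- r = 0: 3/5 = 60%
- r = 0.5: 4/5 = 80%
- r = 0.6: 4.2/5 = 84%
- r = 0.7: 4.4/5 = 88%

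Under Reading B with the same two relapses, those left at V24 show 3/3 = 100%, against 3/5 of all enrolled.

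**5. How likely is at least one case?** The documents give no rate. For an assumed chance p per subject of starting new treatment in follow-up, 1 - (1 - p)^5 gives 41% at p = 0.1, 67% at 0.2, 83% at 0.3 and 92% at 0.4.

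**The case against.** **The plan is not silent on drugs after week 4.** A reader might infer that other treatment is controlled only in the treatment phase, and that every re-treated relapse is scored as lasting benefit. The documents do not support that. On its face, 4.5 bars antidepressants from continuation, and 8.0 permits removal. What stands is that 4.5 conflicts with 3.4 and Appendix A, removal under 8.0 is optional, and applying it replaces masking with selective loss.

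**Treatment is recorded.** A reader might also infer that psychotherapy goes uncaptured. Section 4.3 does list a concomitant therapy review, although 4.5 and Appendix B speak of medication, so its scope is unclear. The records make the remedy cheap, but no planned analysis uses them.

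**Section 6.3 already warns that improvement may not be due to treatment.** Its wording is broad enough to cover co-treatment. It is a general caution for an uncontrolled design, and it does not separate persistence from re-treatment. That can be done subject by subject without a control arm.

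**Masking is limited.** A relapse present at week 1 or 4 would show at V22 or V23. This is fair. Complete masking needs relapse and recovery between ratings, most plausibly in the 8 weeks between V23 and V24. An earlier dip would be visible, but the V24 contrast would still count the recovery.

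**The 84-88% figures are soft.** The plan reports no persistence proportion. Section 1.1 says optimizing a strategy can take 3 to 4 months, longer than the time left before V24. Subjects with treatment-resistant depression may respond less often. These figures are the top of a range, not an estimate of bias.

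**Conclusion.** The concern holds in a limited form. The durability analysis has no rule for antidepressant treatment or psychotherapy started or changed after the last session. A re-treated relapse can therefore be counted as persistence. If 4.5 and 8.0 are applied in follow-up, V24 instead describes mainly those who stayed well. Both routes tend toward concluding that the effect lasts.

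One masked relapse moves the mean change by 2 to 6 CDRS-R points for assumed relapses of 10 to 30 points. With an assumed 2 of 5 relapses, apparent persistence lies between 60% (no response by V24) and 88%. The rate of re-treatment, the size of a relapse and the response by V24 are all assumptions. The direction follows only if those losing benefit are the likelier to be re-treated. This is a worthwhile, inexpensive improvement to the plan and does not invalidate the pilot.

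**What to change.** **In 6.2 and 6.3**, before any follow-up data are seen:
- Classify each subject at V22, V23 and V24 as persisted without new or increased treatment since V21, persisted with it, or not persisted. State the score rule that defines persisted.
- List treatment changes by subject, with dates and reasons.
- Show CDRS-R and HAM-D both as all observed and only up to the last rating before any change. Describe durability as an iTBS effect only with both displays side by side.

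**In 4.3, 4.5 and Appendix B**, make explicit that the existing follow-up review records psychotherapy start, stop and intensity.

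**Reconcile** 3.4, 4.5, 8.0 and Appendix A on antidepressant use and on whether they apply in follow-up. None of the analysis changes requires restricting care.

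**Cost.** A few sentences, one line on an existing form and no extra visits. Durability may look less favourable. Changes made for reasons other than relapse will also be flagged, which is why the classes should be shown in full. Whether only untreated persistence supports Hypothesis 2 is a choice of estimand for the investigators to state.
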